Dates of Analytical Portion :

Method Validation : December 2018
Sample Analysis : After completion of Period 1 and 2

Objectives

The objective of this study is to investigate whether 2 mg cyproterone acetate and 0.035 mg ethinyl estradiol film-coated tablet (**Elzsa[®]**) manufactured by PT. Sydna Farma is bioequivalent to its reference product, Diane[®]-35 sugar-coated tablet manufactured by Bayer Weimar GmbH, Germany for Bayer Pharma AG, Germany, **imported by PT. Bayer Indonesia, Depok, Indonesia.**

PharmaMetric Labs**Study Centre, Clinical Study Laboratory, Analytical Laboratory, Pharmacokinetics and Statistical Analysis Laboratory:**

PT. Pharma Metric Labs
 [name]
 [name]
 [name]
 Indonesia
 [contact]
 [contact]

Medical Screening (blood and urine) Laboratory:

Pramita Clinical Laboratory
 [name].
 [contact]
 [contact]

Sponsor

PT. Sydna Farma
 [name]
 [name]
 Indonesia
 [contact]
 [contact]

Study design

Randomized, single blind, two period, single dose, cross-over study with three weeks washout period in 24 healthy female subjects under fasting condition.

The overall clinical study requires approximately 8 weeks to be completed. The drug allocation information is limited to the Data Management Officer only.

If the above study results in the conditions below, the study could be continued to the second stage with a minimum 12 subjects addition. The second stage study's pharmacokinetics will be statistically analyzed within 94.12% confidence interval. The conditions are:

1. The first stage study has demonstrated bioequivalence, but the number of subjects is not adequate to fulfill 80% power study calculated from the intra subject CV of AUC_t obtained; OR
2. The first stage study has resulted in non-bioequivalence but the geometric mean ratio of the AUC_t falls within 90-110%, and it is probable to have bioequivalence result if the study is continued to the second stage.

The subjects are enrolled in the study under the following inclusion criteria: healthy female subjects with absence of significant disease or clinically significant abnormal laboratory values on laboratory evaluation, medical history or physical examination during screening, aged between 18 – 55 years, body mass index between 18–25 kg/m², have a normal electrocardiogram, blood pressure within normal range (90-120 mmHg for systolic blood pressure and 60-80 mmHg for diastolic blood pressure), heart rate within normal range (60-100 bpm), pass hormone screening related to cyproterone and ethinyl estradiol, and have read the subject information and signed the informed

consent documents. Investigator or Responsible Physician judgment is required to determine subject's eligibility upon clinically insignificant abnormal results.

Exclusion criteria include pregnancy and nursing condition, hypersensitivity to cyproterone acetate and ethinyl estradiol, or other oral contraceptive or other ingredients in the drugs and allergic history, medical condition which might significantly influence the pharmacokinetic of the study drug e.g. chronic gastrointestinal disease, diarrhea, gastric surgery, renal insufficiency, hepatic dysfunction, or cardiovascular disease, history or present of coagulation disorder, thrombophlebitis, and thromboembolic disorder, history of active ulcer, use of any medication one week prior to the study, participation in any clinical study within 3 months prior to the study (< 90 days), donation or lost 300 ml (or more) of blood within 3 months prior to the study, smoke, positive to HIV, HBsAg and HCV tests, history of drug or alcohol abuse within 12 months prior to the study, and likelihood to be non-compliant to the protocol.

Medical history, physical examination, laboratory tests (routine hematology, blood biochemistry and urinalysis), electrocardiograph, pregnancy test and HIV, HBsAg, and HCV tests are carried out to screen the subjects and to obtain eligible subjects who meet the inclusion and exclusion criteria.

Test Drug, Reference Drug, Dose and Mode of Administration:

The reference drug is the commercially available sugar-coated tablet containing 2 mg cyproterone acetate and 0.035 mg ethinyl estradiol, Diane[®]-35, manufactured by Bayer Weimar GmbH, Germany for Bayer Pharma AG, Germany, **imported by PT. Bayer Indonesia, Depok, Indonesia**, reg number: DKI0868204416A1, batch number: 71533A, manufacturing date: March 2017, and expiration date: March 2020.

The test drug is film-coated tablet containing 2 mg cyproterone acetate and 0.035 mg ethinyl estradiol (**Elzsa[®]**) manufactured by PT. Sydna Farma, batch number: TR20745, manufacturing date: August 2018, and expiration date: August 2020.

A single dose of the drug (either test or reference according to randomization code) will be given orally to the subjects in sitting posture. The drug will be administered with 240 ml of water.

Study Procedures

The subjects are instructed to abstain from taking any medication for at least 1 week before and during the study period. They are not permitted to smoke, consume alcohol, milk, beverages or food containing xanthines, such as tea, coffee, chocolate, cola, or fruit juice for 24 hours prior to the study day and during the entire sampling day until the last blood sample is completely collected.

Subjects are admitted into the study wards in PT. Pharma Metric Labs in the evening before drug administration. The subjects will have dinner and fast overnight from 8 hours prior drug administration, and continued until 4 hours after the administration. Water can be consumed as desired except during the period of 1 hour before and 2 hours after drug administration.

In the following morning, as scheduled, subjects are given a single dose of cyproterone acetate + ethinyl estradiol of either formulation (test or reference) with 240 ml of water in sitting posture. Subjects are then asked to maintain upright position (standing or sitting) for 1 hour after drug administration.

Blood samples for cyproterone acetate and ethinyl estradiol assay (approximately 6 ml) are drawn into tubes containing anticoagulant (EDTA) before drug administration (0 h) and 15, 30, 45 min, 1, 1.5, 2, 2.5, 3, 4, 5, 6, 9, 15, 24, 36, 48 and 72 hours after drug administration. Whole blood samples

PharmaMetric Labs

are collected from fresh clean venipuncture using disposable sterile syringe and needle. Collected blood samples are centrifuged at 3000 rpm for 10 minutes using 32-cm rotor diameter centrifuge. Separated plasma is then stored frozen at a maximum temperature of -20°C until assayed.

Standardized meals are served 4 hours after drug administration. A record of the menu served and meal taken by subjects at every study period will be maintained.

After a washout period of three weeks, the study will be repeated in the same manner with the alternate drug.

The subjects' safety is monitored during the entire study. They are under direct supervision by Study Physician at the study site. Vital signs (blood pressure, pulse, respiration rate and body temperature) are monitored and recorded in the Case Report Form.

Analytical Procedures

Plasma concentration of cyproterone acetate and ethinylestradiol will be measured by a validated LC-MS/MS method.

Plasma containing cyproterone acetate and ethinyl estradiol is spiked with internal standard solution and blended well. The drug is then extracted using an organic solvent. The organic layer is transferred to a clean glass tube and evaporated to dryness under nitrogen stream in a water bath. The residue is then reconstituted with organic solvent and an aliquot is injected into the LC-MS/MS system. The LLOQ is 0.4 ng/ml and 4.99 pg/ml for cyproterone acetate and ethinylestradiol, respectively.

Statistical Procedures

The area under the cyproterone acetate and ethinylestradiol concentration versus time curve from 0 to 72 hours (AUC_t) is then calculated using trapezoidal rule. Bioequivalence of the two formulations will be assessed by comparing the AUC_t and C_{max} of cyproterone acetate and ethinyl estradiol values after ln transformation of the concentration data. The geometric mean ratios (test/reference) of the ln-transformed data and their 90% confidence intervals will be further analyzed with a parametric method (analysis of variance/ANOVA) using Equiv Test[®] version 2.0 (Statistical Solution Ltd., Saugus, MA, USA), or manual calculation which has been validated to Equiv Test[®].

Bioavailability Parameters and Bioequivalence Criteria

The two products are considered bioequivalent when the 90% confidence intervals of the cyproterone acetate and ethinyl estradiol geometric mean ratio between test and reference product fall within the range of 80.00-125.00% for AUC_t and C_{max} .

4. ABBREVIATION AND DEFINITION OF TERMS

Symbol	Meaning
AE	adverse event
AUC _t	area under the plasma concentration-time curve
BMI	body mass index
CI	confidence interval
C _{max}	maximum observed plasma concentration
CRF	case report form
EMA	European Medicines Agency
Exp	Expiration
fax	facsimile
GCP	good clinical practice
HBsAg	hepatitis B surface antigen
HCV	hepatitis C virus
HIV	human immunodeficiency virus
Inf	infinity
k _e	terminal elimination rate constant
L	litre
LC-MS/MS	liquid chromatography tandem with mass spectroscopy
LLOQ	lower limit of quantitation
ln	lon
Mfg	manufacturing
mL	mililitre
ng	nanogram
N.A	not available
NADFC	National Agency of Drug and Food Control
No.	number
QA	quality assurance
SAE	serious adverse event
SGOT	serum glutamic oxaloacetic transaminase
SGPT	serum glutamic pyruvic transaminase
t _{1/2}	half-life, associated with terminal slope
tel	telephone
t _{max}	time to attain maximum observed plasma concentration
US FDA	United States of America Food and Drug Administration

5. INTRODUCTION

The presence of a great number of commercially available formulations with the same active ingredient allows the consumers to choose alternative formulations with competitive price. However, those formulations must be proven bioequivalent to the reference drug. The method of choice to demonstrate the equivalence is to conduct a comparative bioavailability study. If the results demonstrate bioequivalence, one may subsequently claim that the therapeutic quality of the formulation and its reference is similar. The latter means that both the benefits and side effects are similar, and hence the formulations are interchangeable.

The quality of pharmaceutical products is dependent on many factors, such as the quality of the raw material, manufacturing process, quality control, packing material, etc. In order to ensure the safety and efficacy of a pharmaceutical product, it is important for the pharmaceutical industry to produce drugs with high standard, especially for drugs made of unstable raw material, low content tablet, and formulations which need special manufacturing technique (e.g. slow release tablet, suppository, etc).

5.1 Pharmacology

Cyproterone acetate blocks the effect of endogenously produced and exogenously administered androgens at the target organs by means of competitive inhibition. This results in a gradual regression of signs of androgenisation, irrespective of whether increased androgen values or increased peripheral sensitivity, are the cause of the disorder. The decrease in androgen concentration at the target organs has an additional therapeutic effect.

Apart from the described antiandrogen effect, cyproterone acetate has also a pronounced progestational action. The combination of ethinylestradiol and cyproterone acetate prevents a possible pregnancy by the inhibition of ovulation, the inspissation of cervical mucus so as to constitute a barrier to sperm, and the rendering of the endometrium unreceptive to implantation.

Dosage of Ethynil Estradiol

Hormone replacement therapy for failure of ovarian development e.g. in patients with gonadal dysgenesis: 10 to 50 micrograms daily, usually on a cyclical basis. Initial estrogen therapy should be followed by combined estrogen/progestogen therapy.

Disorders of menstruation: 20 to 50 micrograms daily from day 5 to day 25 of each cycle. A progestogen is given daily in addition, either throughout the cycle or from days 15 to 25 of the cycle.

If a dose is forgotten it should be taken as soon as it is remembered. If it is nearly time for the next dose then the patient should wait until then. Two doses should not be taken together. Forgetting a dose may increase the likelihood of break-through bleeding and spotting.

5.2 Pharmacokinetic properties

Absorption

Following oral administration cyproterone acetate (CPA) is completely absorbed over a wide dose range. Peak serum concentrations of 15 ng/mL are reached at about 1.6 hours after single ingestion. The absolute bioavailability of cyproterone acetate is unknown. Relative bioavailability was calculated, in a study of eight young women, from a dose-corrected comparison of area under the curves (AUC) of serum levels after 100 mg oral and 300 mg intramuscular depot administration and was found to be 80 + 30% when averaged over all volunteers (range 23% - 119%).

Orally administered ethinylestradiol is rapidly and almost completely absorbed. Peak serum concentrations of about 71 pg/mL are reached within 1-2 hours. Absolute bioavailability, as a result of presystemic conjugation and first pass metabolism, is approximately 60%.

Distribution

Cyproterone acetate is almost exclusively bound to serum albumin. Only 3.5 - 4.0% of the total serum drug concentrations are present as free steroid. The ethinylestradiol-induced increase in sex hormone binding globulin (SHBG) does not influence the serum protein binding of cyproterone acetate. The apparent volume of distribution of cyproterone acetate is about 986 ± 437 L.

Ethinylestradiol is highly but non-specifically bound to serum albumin (approximately 98.5%) and induces an increase in the serum concentrations of SHBG. An apparent volume of distribution of approximately 5 L/kg was determined.

Metabolism

Cyproterone acetate is subject to extensive metabolism. The main metabolite in plasma was identified as 15-hydroxy-CPA which is formed possibly via the cytochrome P450 enzyme CYP3A4. The clearance rate from serum is about 3.6 mL/min/kg.

Ethinylestradiol is subject to presystemic conjugation in both small bowel mucosa and the liver. Ethinylestradiol is primarily metabolized by aromatic hydroxylation but a wide variety of hydroxylated and methylated metabolites are formed, and these are present as free metabolites and as conjugates with glucuronides and sulfate. The metabolic clearance rate is about 5 mL/min/kg.

Elimination

Cyproterone acetate serum levels decrease in two phases which are characterized by half-lives of about 0.8 h and about 2.3 to 3.3 days. Cyproterone acetate is partly excreted in unchanged form. Its metabolites are excreted at a urinary to biliary ratio of about 1:2. The half-life of metabolite excretion is about 1.9 days.

Ethinylestradiol serum levels decrease in two phases, the terminal disposition phase is characterised by half-life of approximately 24 hours. Unchanged drug is not excreted, ethinylestradiol metabolites are excreted at a urinary to biliary ratio of 4:6. The half-life of metabolite excretion is about 1 day.

A bioequivalence study to compare the test product, 2 mg cyproterone acetate/0.035 mg ethinylestradiol fixed-dose tablets and the reference product Diane 35[®] (2 mg cyproterone acetate/0.035 mg ethinylestradiol fixed-dose tablets, Schering France), was performed. The study design was two-way, open, randomised, cross-over study in 35 female postmenopausal healthy volunteers (aged 35-65 years) after single oral dose. The study was clinically well tolerated. The pharmacokinetic parameters of ethinylestradiol are illustrated in Table I and the parameters of cyproterone acetate in Table II.

Table I. Pharmacokinetic parameters of ethinylestradiol

Pharmacokinetic parameters of ethinylestradiol (n=30)			
	Test product	Diane 35 [®]	90% CI
AUC _{0-t} (pg.h/ml)	2044.34 ± 761.49	2026.55 ± 612.80	92.21 – 104.66
AUC _{0-∞} (pg.h/ml)	2274.67 ± 849.00	2229.15 ± 682.69	93.40 – 106.27
C _{max} (pg/ml)	169.23 ± 52.09	177.49 ± 58.72	91.94 – 100.29
t _½ (h)	16.07 ± 4.76	16.82 ± 5.39	
t _{max} (h)	2.0 ± 0.75	2.00 ± 0.50	

Table II. Pharmacokinetic parameters of cyproterone acetate

Pharmacokinetic parameters of cyproterone acetate (n=30)			
	Test product	Diane 35 [®]	90% CI
AUC _{0-t} (pg.h/ml)	318206.1 ± 78626.9	327887.3 ± 85063.0	94.08 – 100.15
AUC _{0-∞} (pg.h/ml)	403149.9 ± 116224.5	428492.9 ± 132888.0	90.70 – 97.75
C _{max} (pg/ml)	27436.24 ± 5872.79	29942.10 ± 7268.07	86.23 – 97.63
t _½ (h)	103.56 ± 24.84	116.81 ± 38.68	
t _{max} (h)	2.00 ± 0.00	1.50 ± 0.50	

A bioequivalence pilot study to compare the test product, 2 mg cyproterone acetate/0.035 mg ethinylestradiol fixed-dose tablets manufactured by PT. Sydna Farma, and the reference product, Diane 35[®] fixed-dose tablets manufactured by Bayer Weimar GmbH, Germany for Bayer Pharma AG, Germany), was performed in 6 healthy female subjects at PT. Pharma Metric Labs, Jakarta. The pharmacokinetic parameters of ethinylestradiol are illustrated in Table III and the parameters of cyproterone acetate in Table IV.

Table III. Pharmacokinetic parameters of ethinylestradiol of the bioequivalence pilot study

Pharmacokinetic Parameter		Test Drug (Lydia [®]) (n = 6) mean (SD)	Reference Drug Diane [®] -35 (n = 6) mean (SD)
Primary	C _{max} (pg.mL ⁻¹)	107.45 (60.00)	86.37 (37.26)
	AUC _t (h.pg.mL ⁻¹)	1020.47 (411.03)	987.75 (479.76)
Secondary	AUC _{inf} (h.pg.mL ⁻¹)	1133.58 (431.60)	1098.46 (592.95)
	T _{max} (h)	1.17 (0.38)	1.83 (0.41)
	T _½ (h)	11.34 (9.04)	9.11 (5.66)

Table IV. Pharmacokinetic parameters of cyproterone acetate of the bioequivalence pilot study

Pharmacokinetic Parameter		Test Drug (Lydia [®]) (n = 6) mean (SD)	Reference Drug Diane [®] -35 (n = 6) mean (SD)
Primary	C _{max} (ng.mL ⁻¹)	18.87 (2.55)	16.47(3.21)
	AUC _t (h.ng.mL ⁻¹)	119.54 (41.35)	116.13 (40.84)
Secondary	AUC _{inf} (h.ng.mL ⁻¹)	127.26 (45.23)	122.32 (42.91)
	T _{max} (h)	1.58 (0.20)	1.67 (0.41)
	T _½ (h)	7.41(3.81)	6.25 (3.66)

5.3 Side-effects

Gastrointestinal	: Nausea, abdominal pain, vomiting, diarrhea
Metabolism and nutrition	: Fluid retention
Psychiatric	: Altered mood, decreased libido, increased libido
Nervous system	: Headache, migraine
Skin and subcutaneous tissue	: Rash, urticaria, erythema nodosum
Reproductive system and breast	: Breast pain, breast hypertrophy, vaginal discharge, breast discharge
Immune system	: Hypersensitivity
Investigations	: Increased weight, decreased weight

The risk of venous thromboembolism (VTE) occurring with these medicines is low and well known, and warnings are included in their product information to alert patients and prescribers to the risks.

There have been no reports of serious deleterious effects from overdose. On the basis of general experience with combined oral contraceptives, symptoms that may occur in case of overdose of active tablets are: nausea, vomiting and, in young girls, slight vaginal bleeding.

6. OBJECTIVES

The primary objective of this study is to find out whether 2 mg cyproterone acetate and 0.035 mg ethinyl estradiol film-coated tablet (**Elzsa[®]**) manufactured by PT. Sydna Farma is bioequivalent to its reference product, Diane[®]-35 sugar-coated tablet manufactured by Bayer Weimar GmbH, Germany for Bayer Pharma AG, Germany, **imported by PT. Bayer Indonesia, Depok, Indonesia.**

7. PRODUCT INFORMATION

7.1 Test product:

Name	: Elzsa [®] film-coated tablet
Active ingredient	: Cyproterone acetate and ethinyl estradiol
Dosage form	: Film-coated tablet
Strength	: 2 mg cyproterone acetate + 0.035 mg ethinylestradiol
Manufacturer	: PT. Sydna Farma
Reg No.	: N.A.
Batch No	: TR20745
Mfg Date	: August 2018
Exp. Date	: August 2020
Dose	: 1 film-coated tablet (administered with approximately 240 ml water)
Batch size	: 200,000 film-coated tablets

7.2 Reference / comparator product

Name	: Diane [®] -35
Active ingredient	: Cyproterone acetate and ethinyl estradiol
Dosage form	: Sugar-coated tablet
Strength	: 2 mg cyproterone acetate + 0.035 mg ethinylestradiol
Manufacturer	: Bayer Weimar GmbH, Germany for Bayer Pharma AG, Germany, imported by PT. Bayer Indonesia, Depok, Indonesia
Reg No.	: DKI0868204416A1
Batch No	: 71533A
Mfg Date	: March 2017
Exp. Date	: March 2020
Dose	: 1 sugar-coated tablet (administered with approximately 240 ml water)

The test batch or lot must be manufactured according to cGMP and originated from a batch of industrial scale. If this is not feasible, a small production batch or pilot batch can be used provided not smaller than 10% of the industrial scale batch, or 100,000 units (whichever is larger).

7.3 Pharmaceutical equivalence data

The pharmaceutical equivalence data will be provided by sponsor. The difference of the assay between test and reference product should not be more than 5%.

7.4 Comparison of dissolution profiles

The result of the comparative dissolution test will be provided by sponsor.

7.5 Letter of Confirmation

Letter of confirmation will be provided by sponsor. This letter confirms that the formula of the product which will be commercially marketed is the same as the formula of the test drug used in the bioequivalence study.

8. INVESTIGATIONAL PLAN

8.1. Study design

Randomized, single blind, two period, single dose, cross-over study with three weeks washout period in 24 healthy female subjects under fasting condition.

The overall clinical study requires approximately 8 weeks to be completed. The drug allocation information is limited to the Data Management Officer only.

If the above study results in the conditions below, the study could be continued to the second stage with a minimum 12 subjects addition. The second stage study's pharmacokinetics will be statistically analyzed within 94.12% confidence interval. The conditions are:

1. The first stage study has demonstrated bioequivalence, but the number of subjects is not adequate to fulfill 80% power study calculated from the intra subject CV of AUC_t obtained; OR
2. The first stage study has resulted in non-bioequivalence but the geometric mean ratio of the AUC_t falls within 90-110%, and it is probable to have bioequivalence result if the study is continued to the second stage.

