8.5. Statistical evaluation

Bioequivalence of the two drug formulations is assessed by calculating individual AUC_t and C_{max} values. The mean ratio (test/reference) of the ln-transformed data and their 90% confidence intervals is analyzed with a parametric method (analysis of variance/ANOVA) using Equiv Test[®] version 2.0 (Statistical Solution Ltd., Saugus. MA, USA) or manual calculation which has been validated to Equiv Test[®]

90% confidence intervals (90% CIs) are calculated using the following equation :

$$(90\% \text{ CI})_{diff} = \text{difference} \pm t_{0.1 (n-2)} \times SE_{diff}$$

$$\text{difference} = \text{mean of ln T} - \text{mean of ln R}$$

PharmaMetric Labs

n = number of subject

$\alpha = 0.05$

$SE\ diff = (\frac{1}{2}MS_{residual} \times (1/nTR + 1/nRT))^{\frac{1}{2}}$

(90% CI) ratio = anti ln (90% CI)_{diff} X 100%

The two products are considered bioequivalent when the 90% confidence interval of the cyproterone acetate and ethinyl estradiol geometric mean ratio between test and reference product falls within the range of 80.00 - 125.00% for AUC_t and C_{max}.

If a pre-dose concentration of cyproterone acetate and ethinyl estradiol is detected, the subject's data can be included in the pharmacokinetic and statistical analysis without adjustment, if the pre-dose concentration is equal to or less than 5% of the C_{max} value of the corresponding period. If the pre-dose concentration is greater than 5% of the C_{max} value, the subject's data will be dropped from all pharmacokinetic and statistical evaluations of cyproterone acetate and ethinyl estradiol.

Subjects who lack of any measurable concentrations, or have only very low plasma concentrations of cyproterone acetate and ethinyl estradiol for the reference medicinal product, will be excluded from statistical analysis. According to EMA Guidance (CPMP/EWP/QWP/1401/98 Rev.1/Corr**), a subject is considered to have very low plasma concentrations if its AUC is less than 5% of reference medicinal product geometric mean, calculated without inclusion data from the outlying subject. Data (concentrations and pharmacokinetic parameters) from these excluded subjects will be presented but excluded from descriptive statistics. If the study is continued to the second stage, the 94.12% confidence intervals (94.12% CIs) are calculated using $\alpha = 0.0294$.

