8.8.3. Ethics approval and amendments

The protocol, the informed consent statement, and advertisement are reviewed by the Independent Ethics Committee of the Medical Faculty, University of Indonesia. Any modification of the protocol which may have any impact on the conduct of the study, potential benefit of the study, or may affect subjects' safety, including changes of the study objective, study design, study population, sample size, study procedure, or significant administrative aspects will require a formal amendment to the protocol. Such amendment has to be agreed upon by the sponsor, the responsible investigator and the Ethics Committee prior to implementation.

Minor administrative changes of the protocol are minor corrections and/or clarifications that have no effect on the way of the study is conducted. These minor administrative changes will be agreed upon by the sponsor and the responsible investigator and will be documented in a memorandum. The Ethics Committee may be notified of the minor administrative changes at the discretion of the responsible investigator.

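### Condition 1 lets a study that has already met the 90% CI criterion continue at 94.12% without saying which result decides, and with stage 1 judged at the full 90% CI the 94.12% level does not hold type I error at 5%

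*Combined protocol and SAP*

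**What the plan says.** The synopsis (Study design) and section 8.1 describe a "cross-over study with three weeks washout period in 24 healthy female subjects under fasting condition". Both add that "the study could be continued to the second stage with a minimum 12 subjects addition" if one of two conditions holds.

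- Condition 1: "The first stage study has demonstrated bioequivalence, but the number of subjects is not adequate to fulfill 80% power study", with power calculated from the observed intra-subject CV of AUC_t.
- Condition 2: the stage-1 result is "non-bioequivalence but the geometric mean ratio of the AUC_t falls within 90-110" per cent, and bioequivalence is judged probable if the study goes on.

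For a continued study, section 8.1 says that the second-stage "pharmacokinetics will be statistically analyzed within 94.12% confidence interval". Section 8.5 repeats the level: "If the study is continued to the second stage, the 94.12% confidence intervals (94.12% CIs) are calculated using" alpha 0.0294.

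The only criterion for a conclusion is in section 8.5 and, in near-identical terms, in the synopsis: "The two products are considered bioequivalent when the 90% confidence interval of the cyproterone acetate and ethinyl estradiol geometric mean ratio" lies within 80.00-125.00% for AUC_t and Cmax.

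The documents do not say whether a stage-1 pass stands or is replaced once stage 2 is run, or whether the 94.12% interval uses pooled or stage-2 data. They also do not give the test/reference ratio for the 80% power check, or say which analyte's AUC_t supplies the CV.

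**The concern.** A two-stage rule needs a defined decision at each stage. Condition 1 reopens a study that has met the stated criterion and applies a stricter interval, with no rule on which interval governs. Neither reading gives the extra stage a useful role for a product that has passed. Under one reading the pass can only be confirmed or lost. Under the other, at least 12 more women are dosed with no possible effect on the conclusion. Continuation is optional, so any protection condition 1 gives against a false pass is not assured.

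The larger statistical issue lies behind this. An alpha of 0.0294 at the final look is a reduced level meant to leave room for an earlier look. Here stage 1 is judged at the full 0.05 per side, and a failing study can be tested again under condition 2. That second chance comes on top of a stage 1 that has already used the whole 5%. Condition 2 also looks only at AUC_t, so a study that failed on Cmax alone can re-enter with no limit on its Cmax ratio.

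**Working it through.** **1. The plan's own figure.** Confidence level = 1 - 2 x alpha = 1 - 2 x 0.0294 = 0.9412. The stated 94.12% reproduces.

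**2. The power trigger.** Inputs: n = 24 (section 8.1), two one-sided tests at 0.05, 22 df, SE = s_w x sqrt(2/n), s_w^2 = ln(1 + CV^2). Exact power falls below 80% once CV exceeds 16.0%, 23.2% or 26.0% at an assumed ratio of 0.90, 0.95 or 1.00. At CV 20% the required total is 38, 20 or 16 subjects, so condition 1 is met only if 0.90 is assumed. At CV 25% it is 56, 28 or 24, so it is met at 0.90 and 0.95 but not at 1.00.

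**3. Variability in the documents.** Tables I and II give 90% CIs with n = 30 (balanced sequences assumed). SE = ln(upper/lower)/(2 x 1.701), with t on 28 df; variance = SE^2 x 30/2; CV = sqrt(exp(variance) - 1).

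- Ethinylestradiol AUC_t: ln(104.66/92.21) = 0.1266; SE 0.0372; variance 0.0208; CV 14.5%.
- Cyproterone acetate AUC_t: ln(100.15/94.08) = 0.0625; SE 0.0184; variance 0.0051; CV 7.1%.
- Cyproterone acetate Cmax: ln(97.63/86.23) = 0.1242; SE 0.0365; variance 0.0200; CV 14.2%.

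The chance that the trigger is met is P(chi-square on 22 df > 22 x ln(1 + limit^2)/ln(1 + CV^2)). With ethinylestradiol AUC_t it is 22%, 0.01% and about 0% at ratio 0.90, 0.95 and 1.00. With cyproterone acetate AUC_t it is 0% at all three.

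**4. One metric.** Simulation with n1 = 24, final analysis at 0.0294 on pooled data with a stage term (n1 + n2 - 3 df), trigger ratio 0.95, and condition 2 always continued. The CVs are hypothetical.

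| | CV 25% | CV 30% | CV 35% |
|---|---|---|---|
| Stage-1 passes meeting condition 1 (true ratio 0.95) | 60% | 89% | 97% |
| Of those, reversed if stage 2 decides, n2 = 12 | 5% | 12% | 22% |
| Same, n2 = 48 | 0.3% | 2% | 5% |
| All studies that pass and meet condition 1 | 44% | 50% | 37% |
| Type I error, condition 1 always followed and stage 2 decides (true ratio 0.80, n2 = 12) | 3.7% | 2.7% | 2.5% |
| Type I error, condition 1 unused or the pass stands (n2 = 12) | 5.1% | 5.4% | 5.5% |

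**5. AUC_t and Cmax both required, only AUC_t gating stage 2.** AUC_t CV 14.5%, Cmax CV 14.2%, true AUC_t ratio 1.00, true Cmax ratio 0.80, other conventions as in step 4. The SD of the observed log AUC_t ratio is sqrt(0.0208) x sqrt(2/24) = 0.0416. The 90-110% window therefore runs from -0.1054/0.0416 = -2.5 to 0.0953/0.0416 = 2.3 SD and is open about 98% of the time. Cmax is in effect tested twice, at 0.05 and then at 0.0294. Type I error is about 6% with n2 = 12 and about 7% with n2 = 48, at correlations of 0, 0.5 and 0.8. Condition 1 does not alter this, because at ratio 0.95 its trigger is met 0.01% of the time.

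**6. The alternatives in the same two-metric case.** Judging stage 1 at 94.12% gives about 4.4% (n2 = 12) and 5.1-5.2% (n2 = 48). A rule that keeps the 90% CI whenever a power check is satisfied gives 6.1% and 6.8-7.0%, no better than the plan, because at these CVs the check is satisfied and stage 1 stays at 90%.

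**The case against.** Section 8.5 ties the 94.12% interval to any continued study, so the natural reading is that this interval decides once stage 2 is run. That stands, and it makes the reading in which women are dosed to no purpose the less likely one. It is still an inference. It also leaves open when continuation is required, and on what ratio and analyte.

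Condition 1 can be defended as protection. If it is always followed and stage 2 decides, 64 to 65% of the false passes that enter are reversed with n2 = 12. A reader might infer that continuing under condition 1 inflates type I error. The documents do not support that: with one metric, following it lowers the error. The excess comes from the full 90% CI at stage 1 combined with the second chance under condition 2.

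The figures also depend on conditions that may not arise. The 25 to 35% CVs are hypothetical, and the documents' own CVs make the trigger almost irrelevant at ratio 0.95. All type I figures assume condition 2 is always continued, although the text makes it optional and requires success to be probable. Both points stand and limit the weight given to the sizes.

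Finally, three sentences could clarify the ratio, the analyte and the deciding interval. That would settle condition 1, but it would leave the 6 to 7% case untouched.

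**Conclusion.** The point holds as a defect in a stated rule, not merely missing detail: under either reading, condition 1 has no useful outcome for a study that has passed. Taken alone its weight is low to moderate, since at the Tables I and II AUC_t CVs and ratio 0.95 it would almost never be triggered.

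The 94.12% level does not deliver 5% control with stage 1 at the 90% CI. The excess is small with one metric (5.1-5.5% at CV 25-35%, condition 1 unused). It reaches about 6 to 7% in the two-metric case, whether or not condition 1 is followed. That case assumes pooled data, a true AUC_t ratio of 1.00 with a true Cmax ratio of 0.80, and condition 2 always continued. It is one unfavourable configuration, not the plan's expected error rate. The simulations cover one or two metrics, whereas the criterion requires four comparisons, so pass rates would be lower if several were borderline.

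The CVs come from a different test product in postmenopausal women, and the six-subject pilot in section 5.2 reports no intra-subject CV. A reader might also infer that adding a power check to stage 1 would repair the plan. It does not hold 5% once Cmax is included.

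**What to change.** - Delete condition 1.
- Judge stage 1 at the 94.12% CI (alpha 0.0294) for AUC_t and Cmax of both analytes.
- State that a pass at that level is final and ends the study.
- Reserve stage 2 for stage-1 failures that meet condition 2, and name the analyte whose AUC_t ratio is meant there.
- State that the deciding stage-2 analysis is the 94.12% CI on pooled data.

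Do not simply delete condition 1 while stage 1 stays at the 90% CI: that is the 5.1-5.5% case above.

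The result is not exact control. In the two-metric case, type I error is about 4.4% with 12 added subjects and 5.1-5.2% with 48, so a large second stage should be checked before it is adopted.

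The cost in probability of success at a true ratio of 0.95 is about 1 point at CV 14.5% and 4 points at CV 20% (one metric). With two metrics it is about 3 to 4 points at Cmax CV 25-30% with 12 added subjects. Some studies that would have ended at stage 1 will need a second stage. No new procedures are needed, but under section 8.8.3 a change of this kind "will require a formal amendment to the protocol".

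If the sponsor keeps a power check instead, it must name the ratio and the analyte, and accept that such a rule does not hold 5% when Cmax is included.
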